### **7.3.7 Definition of an Overdose for this Protocol and Reporting of Overdose to the Study PI and Merck**

For purposes of this study, an overdose of pembrolizumab will be defined as any dose of 1,000 mg or greater ( $\geq 5$  times the indicated dose). No specific information is available on the treatment of overdose of pembrolizumab. In the event of overdose, the participant should be observed closely for signs of toxicity. Appropriate supportive treatment should be provided if clinically indicated.

If an adverse event(s) is associated with ("results from") the overdose of a Merck product, the adverse event(s) is reported as a serious adverse event, even if no other seriousness criteria are met.

If a dose of Merck's product meeting the protocol definition of overdose is taken without any associated clinical symptoms or abnormal laboratory results, the overdose is reported as a non-serious Event of Clinical Interest (ECI), using the terminology "accidental or intentional overdose without adverse effect."

All reports of overdose with and without an adverse event must be reported within 24 hours to the Sponsor and within 2 working days hours to Merck Global Safety. [REDACTED]

### 7.3.7.1 Event of Clinical Interest

Selected non-serious and serious adverse events are also known as Events of Clinical Interest (ECI) and must be reported within 2 working days to Merck Global Safety. [REDACTED]

For the time period beginning when the consent form is signed until treatment allocation/randomization, any ECI, or follow up to an ECI, that occurs to any participant must be reported within 2 working days to Merck Global Safety if it causes the participant to be excluded from the trial, or is the result of a protocol-specified intervention, including but not limited to washout or discontinuation of usual therapy, diet, placebo treatment or a procedure.

For the time period beginning at treatment allocation/randomization through 90 days following cessation of treatment, or 30 days following cessation of treatment if the participant initiates new anticancer therapy, whichever is earlier, any ECI, or follow up to an ECI, whether or not related to Merck product, must be reported within 2 working days to Merck Global Safety.

Events of clinical interest for this trial include:

1. an overdose of Merck product, as defined in Section - Definition of an Overdose for This Protocol and Reporting of Overdose to the Sponsor, that is not associated with clinical symptoms or abnormal laboratory results.
2. an elevated AST or ALT lab value that is greater than or equal to 3X the upper limit of normal and an elevated total bilirubin lab value that is greater than or equal to 2X the upper limit of normal and, at the same time, an alkaline phosphatase lab value that is less than 2X the upper limit of normal, as determined by way of protocol-specified laboratory testing or unscheduled laboratory testing.\*

\*Note: These criteria are based upon available regulatory guidance documents. The purpose of the criteria is to specify a threshold of abnormal hepatic tests that may require an additional evaluation for an underlying etiology.

### 7.3.8 Adverse Events Monitoring

Refer to the Data Safety Monitoring Plan, located in Appendix 2.

### 7.3.9 Expedited Reporting

#### **Reporting to the Data and Safety Monitoring Committee**

If a death occurs during the treatment phase of the study or within 30 days after the last administration of the study drug(s) and it is determined to be related either to the study drug(s) or to a study procedure, the Investigator or his/her designee must notify the DSMC Chair (or qualified alternate) within 1 business day of knowledge of the event. The contact may be by phone or e-mail.

#### **Reporting to Institutional Review Board**

The UCSF PI must report events to the UCSF IRB according to institutional guidelines.

UCSF IRB website for guidance in reporting adverse events: <https://irb.ucsf.edu/adverse-event>

## **Reporting to Sponsor – Merck & Co**

Any serious adverse event, that are unexpected and related, or follow up to a serious adverse event, including death due to any cause other than progression of the cancer under study that occurs to any subject from the time the consent is signed through 30 days following cessation of treatment if the subject initiates new anticancer therapy, whichever is earlier, whether or not related to the Sponsor's product, must be reported within 24 hours to the Sponsor either by electronic media or paper. Sponsor Contact information can be found in the Investigator Trial File Binder (or equivalent).

Additionally, any serious adverse event, considered by an investigator who is a qualified physician to be related to the Sponsor's product that is brought to the attention of the investigator at any time outside of the time period specified in the previous paragraph also must be reported immediately to the Sponsor.

## **Expedited Reporting to the FDA**

If the study is being conducted under an IND, the Sponsor (or the Sponsor-Investigator) is responsible for determining whether or not the suspected adverse reaction meets the criteria for expedited reporting in accordance with federal regulations (21 CFR §312.32).

The Sponsor (or Sponsor-Investigator) must report in an IND safety report any suspected adverse reaction that is both serious and unexpected. The Sponsor needs to ensure that the event meets all three definitions:

- Suspected adverse reaction
- Unexpected
- Serious

If the adverse event does not meet all three of the definitions, it should not be submitted as an expedited IND safety report.

The timeline for submitting an IND safety report to FDA is no later than **15 calendar days** after the Investigator determines that the suspected adverse reaction qualifies for reporting (21 CFR 312.32(c)(1)).

Any unexpected fatal or life-threatening suspected adverse reaction will be reported to FDA no later than **7 calendar days** after the Investigator's initial receipt of the information (21 CFR 312.32(c)(2)).

Any relevant additional information that pertains to a previously submitted IND safety report will be submitted to FDA as a Follow-up IND Safety Report without delay, as soon as the information is available (21 CFR 312.32(d)(2)).

## **Reporting to Industry Partners**

### **Reporting of Pregnancy and Lactation to the Sponsor and Merck**

Although pregnancy and infant exposure during breastfeeding are not considered adverse events, it is the responsibility of investigators or their designees to report any pregnancy or lactation in a participant (spontaneously reported to them) that occurs during the study.

Pregnancies and infant exposures during breastfeeding that occur after the consent form is signed but before treatment allocation/randomization must be reported by the investigator if they cause the participant to be excluded from the trial, or are the result of a protocol-specified

intervention, including but not limited to washout or discontinuation of usual therapy, diet, placebo treatment or a procedure.

Pregnancies and infant exposures during breastfeeding that occur from the time of treatment allocation/randomization through 120 days following cessation of Sponsor's product, or 30 days following cessation of treatment if the participant initiates new anticancer therapy, whichever is earlier, must be reported by the investigator. All reported pregnancies must be followed to the completion/termination of the pregnancy. Pregnancy outcomes of spontaneous abortion, missed abortion, benign hydatidiform mole, blighted ovum, fetal death, intrauterine death, miscarriage, and stillbirth must be reported as serious events (Important Medical Events). If the pregnancy continues to term, the outcome (health of infant) must also be reported.

Such events must be reported within 24 hours to the Sponsor and within 2 working days to Merck Global Safety. [REDACTED]

## 8 Statistical Considerations and Evaluation of Results

This is a randomized two-arm trial with futility early stopping built-in within each treatment arm using a Simon's two-stage design (Simon, 1989). The effect of vorinostat on pembrolizumab and the effect of pembrolizumab and tamoxifen in this biomarker-selected population of ER+ breast cancer patients will be first tested against the respectively chosen null rate in the first stage within the treatment arms and then compared between the treatment arms.

### 8.1 Sample Size Considerations

#### 8.1.1 Sample Size and Power Estimate

For Arm A (pembro + vorinostat + TAM): The null hypothesis that the true response rate for pembrolizumab and vorinostat in ER+ pretreated patients alone without biomarker enrichment is 0.15 which will be tested against the alternative that response rate of pembrolizumab in a biomarker select population is 0.40. In the first stage, 13 patients will be accrued. If there are 2 or fewer responses in these 13 patients, the study will be stopped. Otherwise, 22 additional patients will be accrued for a total of 35. The null hypothesis will be rejected if 10 or more responses are observed in 35 patients. This design yields a type I error rate of 0.025 and power of 0.9 in this treatment arm when the true response rate is 0.4 in this patient subpopulation.

For Arm B (pembro + TAM): The null hypothesis that the true response rate for pembrolizumab in ER+ pretreated patients alone is 0.10 which will be tested against the alternative that response rate of pembrolizumab in a biomarker select population is 0.35. In the first stage, 11 patients will be accrued. If there are 1 or fewer responses in these 11 patients, the study will be stopped. Otherwise, 19 additional patients will be accrued for a total of 30. The null hypothesis will be rejected if 7 or more responses are observed in 30 patients. This design yields a type I error rate of 0.025 and power of 0.9 in this treatment arm when the true response rate of pembro and TAM treatment is 0.35 in this patient subpopulation.

Based on earlier results in Section 1.3 and hypothesized treatment effects, we will most likely to enroll 46 evaluable patients (~65% chance), whereas the possible enrollment ranges from 24 to 65. For the comparison of the treatment arms, the proposed design will have 72.53% power for the Fisher's exact test at 0.1 significance level when the true response rates are 0.4 and 0.1 for the immune priming and the no immune priming treatment arm.

### 8.1.2 Randomization

This is an open-label randomized trial; therefore, the sponsor, investigator, and subject will know the treatment administered. Two arms will be tested, with each independent assessment. Patients will be randomized to either arm using a computerized randomization program by [name].

### 8.1.3 Stratification Factors

Patients will be stratified by prior number of chemo- and hormonal therapies.

### 8.1.4 Accrual Estimates

Ten patients are expected to be eligible yearly based on prior accrual for a similar population.

## 8.2 Interim Analyses and Stopping Rules

This is a randomized two-arm trial with futility early stopping built-in within each treatment arm using a Simon's two-stage design.

In addition to the interim analysis for efficacy that is built into the Simon 2-stage design (see above), in each arm, we will evaluate the need for dose modification after 6 patients have been enrolled. If 2 or more patients have a grade 3 non-hematologic toxicity that is clearly related to pembrolizumab, this agent will be reduced to 75%. Dose modification of vorinostat should be undertaken as per dose modification guidelines, a prior study with vorinostat and tamoxifen suggest that there is a high interpatient variability and tolerance and vorinostat will be adjusted per dose modification guidelines individually.

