## **5 Treatment Plan**

### **5.1 Dosage and Administration**

All trial treatments will be administered on an outpatient basis.

Pembrolizumab 200 mg will be administered as a 30-minute IV infusion every 3 weeks. Treatment cycle intervals may be increased due to toxicity, as described in Section 5.2. Every effort should be made to target infusion timing to be as close to 30 minutes as possible. However, given the variability of infusion pumps, a window of -5 minutes and +10 minutes is permitted (i.e., infusion time is 30 minutes: -5 min/+10 min).

The Pharmacy Manual contains specific instructions for the preparation of the pembrolizumab infusion fluid and administration of infusion solution.

Selection of 200 mg as the appropriate dose for a switch to fixed dosing is based on simulation results indicating that 200 mg will provide exposures that are reasonably consistent with those obtained with 2 mg/kg dose and importantly will maintain individual patient exposures within the exposure range established in melanoma as associated with maximal clinical response. A population PK model, which characterized the influence of body weight and other patient covariates on exposure, has been developed using available data from 476 subjects from PN001. The distribution of exposures from the 200 mg fixed dose is predicted to considerably overlap those obtained with the 2 mg/kg dose, with some tendency for individual values to range slightly higher with the 200 mg fixed dose. The slight increase in PK variability predicted for the fixed-dose relative to weight-based dosing is not expected to be clinically important given that the range of individual exposures is well contained within the range of exposures shown in the melanoma studies of 2 and 10 mg/kg to provide similar efficacy and safety. The population PK evaluation revealed that there was no significant impact of tumor burden on exposure. In addition, exposure was similar between the NSCLC and melanoma indications. Therefore, there are no anticipated changes in exposure between different tumor types and indication settings. As vorinostat and tamoxifen are oral, self-administered drugs, drug diaries will be provided for assessing compliance with treatment. The diary will be provided each time vorinostat and tamoxifen are provided to the study participant to take home. Missed doses will be noted and will not be replaced. The participant will proceed with the next scheduled dose at the next scheduled time.

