## 5.2 Dose Modifications and Dosing Delays

The following dose modification rules will be used with respect to potential toxicity. Toxicity will be assessed according to the NCI CTCAE version 5.0.

The following dose modifications should be made for febrile neutropenia, and blood counts obtained on day one of each cycle. If more than one of these conditions applies, use the most stringent (i.e., the greatest dose reduction). **The AE may be due to pembrolizumab or vorinostat alone in which case the respective agent should be reduced. If overlapping toxicity is suspected, both drugs may be reduced with the potential to re-escalate the non-offending agent. Given the very different nature of pembrolizumab and vorinostat/tamoxifen toxicities, separate tables are shown for individual agents.**

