**Gastrointestinal Toxicity**

**Nausea/Vomiting/Dehydration:** In this protocol, the routine use of any and all anti-emetics is allowed as clinically appropriate; these include the use of dexamethasone and 5-HT3 receptor antagonists.

Patients should maintain adequate fluid and food intake because vorinostat's dose-limiting toxicities are anorexia, dehydration, diarrhea, and fatigue. In the setting of dysgeusia, popsicles and Gatorade have been found to be useful by some investigators to maintain adequate hydration. Patients should also be encouraged to seek a nutritional consult.

**Diarrhea:** Treat diarrhea promptly with appropriate supportive care, including loperamide. Instruct patients to begin taking loperamide at the first signs of 1) poorly formed or loose stool, 2) occurrence of more bowel movements than usual in one day, or 3) unusually high volume of stool. Loperamide should be taken in the following manner: 4 mg at first onset of diarrhea then 2 mg after each unformed stool. The daily dose should not exceed 16 mg. Loperamide should not be taken prophylactically. Advise patients to drink plenty of clear fluids to help prevent dehydration caused by diarrhea. Avoid loperamide if there is the presence of blood or mucus in the stool or if diarrhea is accompanied by fever. If diarrhea is suspected to be linked to pembrolizumab and is ≥ grade 3, hold dose until toxicity resolves to ≤ grade 1, then resume at dose given in prior cycle.

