#### **Restarting Study Interventions:**

Participants may not have any dose modifications (no change in dose or schedule) of pembrolizumab in this study, as described in Table 5.4.

- If the toxicity does not resolve or the criteria for resuming treatment are not met, the participant must be discontinued from all study interventions.
- If the toxicities do resolve and conditions are aligned with what is defined in Table 5.4, the combination of Vorinostat, Tamoxifen and pembrolizumab may be restarted at the discretion of the investigator. In these cases where the toxicity is attributed to the combination or to Vorinostat or Tamoxifen alone, re-initiation of pembrolizumab as a monotherapy may be considered at the PI's discretion.

**Table 5.4 Dose modification and toxicity management guidelines for immune-related AEs associated with pembrolizumab monotherapy and IO Combinations**

irAEs	Toxicity Grade (CTCAE v5.0)	Action With Pembrolizumab	Corticosteroid and/or Other Therapies	Monitoring and Follow-up
Pneumonitis	Grade 2	Withhold	
 
• Administer corticosteroids (initial dose of 1 to 2 mg/kg prednisone or equivalent) followed by taper
 
• Add prophylactic antibiotics for opportunistic infections
 
	
 
• Monitor participants for signs and symptoms of pneumonitis
 
• Evaluate participants with suspected pneumonitis with radiographic imaging and initiate corticosteroid treatment
 

	Recurrent Grade 2, Grade 3 or 4	Permanently discontinue		
Diarrhea/Colitis	Grade 2 or 3	Withhold	
 
• Administer corticosteroids (initial dose of 1 to 2 mg/kg prednisone or equivalent) followed by taper
 
	
 
• Monitor participants for signs and symptoms of enterocolitis (ie, diarrhea, abdominal pain, blood or mucus in stool with or without fever) and of bowel perforation (ie, peritoneal signs and ileus)
 
• Participants with ≥Grade 2 diarrhea suspecting colitis should consider GI consultation and performing endoscopy to rule out colitis
 
• Participants with diarrhea/colitis should be advised to drink liberal quantities of clear fluids. If sufficient oral fluid intake is not feasible, fluid and electrolytes should be
 

	Recurrent Grade 3 or Grade 4	Permanently discontinue		

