**Note: Non-irAE will be managed as appropriate, following clinical practice recommendations.**

a AST/ALT: >3.0 to 5.0 x ULN if baseline normal; >3.0 to 5.0 x baseline, if baseline abnormal; bilirubin:>1.5 to 3.0 x ULN if baseline normal; >1.5 to 3.0 x baseline if baseline abnormal

b AST/ALT: >5.0 to 20.0 x ULN, if baseline normal; >5.0 to 20.0 x baseline, if baseline abnormal; bilirubin:>3.0 to 10.0 x ULN if baseline normal; >3.0 to 10.0 x baseline if baseline abnormal

c AST/ALT: >20.0 x ULN, if baseline normal; >20.0 x baseline, if baseline abnormal; bilirubin: >10.0 x ULN if baseline normal; >10.0 x baseline if baseline abnormal

d The decision to withhold or permanently discontinue pembrolizumab is at the discretion of the investigator or treating physician. If control achieved or ≤ Grade 2, pembrolizumab may be resumed.

e Events that require discontinuation include, but are not limited to: encephalitis and other clinically important irAEs (e.g., vasculitis and sclerosing cholangitis).

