**Table 5.6 Recommended Approach to Handling Pneumonitis**

Study drug associated pneumonitis	Withhold/Discontinue pembrolizumab	Supportive Care
Grade 1 (asymptomatic)	No action	Intervention not indicated
Grade 2	Withhold pembrolizumab, may return to treatment if improves to Grade 1 or resolves within 12 weeks	Systemic corticosteroids are indicated. Taper if necessary.
Grade 3 and Grade 4	Discontinue pembrolizumab	Systemic corticosteroids are indicated. The use of infliximab may be indicated as appropriate. Refer to the Event of Clinical Interest and Immune-related Adverse Event Guidance Document for additional recommendations.

For Grade 2 pneumonitis that improves to  $\leq$  Grade 1 within 12 weeks, the following rules should apply:

- First episode of pneumonitis
  - May increase dosing interval by one week in subsequent cycles
- Second episode of pneumonitis – permanently discontinue pembrolizumab if upon rechallenge subject develops pneumonitis  $\geq$  Grade 2

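### The six-patient toxicity rule in 8.2 orders a pembrolizumab dose cut that 5.2.2 does not allow for immune-related events, and its trigger says grade 3 without adding or higher

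*Combined protocol and SAP*

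**What the plan says.** Section 8.2 adds a toxicity look in each arm once six patients are enrolled: "If 2 or more patients have a grade 3 non-hematologic toxicity that is clearly related to pembrolizumab, this agent will be reduced to 75" percent. Vorinostat is left to individual adjustment.

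Section 5.2.2, under Restarting Study Interventions, says: "Participants may not have any dose modifications (no change in dose or schedule) of pembrolizumab in this study, as described in Table 5.4". Table 5.4, which covers immune-related events, lists three actions for pembrolizumab: continue, withhold, or permanently discontinue. A note below it leaves non-immune events to clinical practice.

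Section 5.2 points the other way: "The AE may be due to pembrolizumab or vorinostat alone in which case the respective agent should be reduced". It adds that both drugs may be reduced when toxicity seems to overlap.

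On schedule, 5.1 says "Treatment cycle intervals may be increased due to toxicity", and Table 5.6 says of a first pneumonitis episode: "May increase dosing interval by one week in subsequent cycles".

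Tables 5.1 to 5.3 list pembrolizumab at 200 mg only.

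**The concern.** The 8.2 rule is the only numeric arm-level toxicity trigger in the protocol, and its action is mandatory. If it is met through immune-related events, one section tells the team to lower the dose and another tells them not to change it. The choice would then be made ad hoc, in an open-label trial, just after two serious toxicities in six patients.

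The count itself is also open to argument. If two patients had related grade 4 events, one reader would say the trigger is met and another that it is not, because the sentence names grade 3 only.

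**Working it through.** The documents give no operating characteristic for the six-patient rule, so there is no stated figure to reproduce. The check is mainly of one text against another.

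**1. Dose implied.** Protocol dose 200 mg every 3 weeks (5.1). 0.75 × 200 mg = 150 mg. No treatment table contains this level, and the protocol does not print the figure.

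**2. Does the trigger reach immune-related events?** It covers any non-hematologic toxicity clearly related to pembrolizumab. The events named in Table 5.4 (pneumonitis, colitis, liver enzyme elevation, endocrine events, nephritis, neurological toxicity, myocarditis, exfoliative skin conditions) are all non-hematologic. Nothing in 8.2 removes them.

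**3. Instructions side by side once the trigger is met.**

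| Events that trip the rule | 8.2 | 5.2.2 and Table 5.4 | 5.2 |
|---|---|---|---|
| Immune-related | Reduce to 150 mg | No change of dose or schedule; continue, withhold or stop | Reduce the responsible agent |
| Non-immune | Reduce to 150 mg | Outside the table; the 5.2.2 sentence still says *in this study* | Reduce the responsible agent |

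The first row is a direct conflict. In the second, only the words *in this study* stand against 8.2.

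**4. Worked case.** Two of six patients in an arm have related grade 3 AST/ALT elevation. Table 5.4 takes both off pembrolizumab permanently, so the 8.2 cut could reach only other patients. For them 8.2 says 150 mg, while the 5.2.2 sentence allows no change. Section 8.2 does not say whether it means current patients, future patients, or one arm or both.

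**5. Literal count by grade.** The threshold is 2.
- Two grade 3 events: count 2, met.
- One grade 3 and one grade 4: count 1, not met.
- Two grade 4 or 5 events: count 0, not met.

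Other places name higher grades when they mean them: the diarrhea text in 5.2 (grade 3 and above), the fatigue table (3 and 4), 7.3.6 (3 to 5), and the adverse event rate review in Appendix 2 (3 or 4). On the other hand, 5.2.1 and 6.5.2 describe severe enterocolitis with a bare grade 3 where grade 4 can hardly be excluded. Loose wording is therefore the likelier explanation.

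**6. Schedule.** Pneumonitis is in Table 5.4, to which the no-change sentence refers, yet Table 5.6 lets the interval grow by a week after a grade 2 episode that improves. Section 5.1 allows longer intervals for toxicity generally. Both disagree with a ban on schedule changes.

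**7. Efficacy design.** With n1 first-stage patients, stop if X1 ≤ r1, and reject if the total is at least r:

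P(reject | p) = Σ over x from r1+1 to n1 of P(X1 = x) × P(X2 ≥ r − x)

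- Arm A (13/35, r1 = 2, r = 10): 0.0249 at p = 0.15 and 0.904 at p = 0.40.
- Arm B (11/30, r1 = 1, r = 7): 0.0220 at p = 0.10 and 0.900 at p = 0.35.

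These agree with the stated 0.025 (a ceiling in Arm B) and 0.9. The toxicity wording does not enter the calculation.

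**The case against.** The strongest reply is about scope. The 5.2.2 sentence sits in the immune-related section, under a heading on restarting treatment, and ends by pointing to Table 5.4. It can be read as governing how one patient resumes after an immune-related hold, with 8.2 as a separate arm-level rule. This stands in part: a reader might infer that the sections collide whenever the trigger fires, and that is not shown for non-immune events. It does not remove the conflict for immune-related events, which the trigger includes.

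Section 3.1 says pembrolizumab will be modified according to the manufacturer's guidelines. That tells a site where to look, but those guidelines are not reproduced in full and the line does not say whether 8.2 or 5.2.2 prevails.

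Two citations that seem to help add little. The diarrhea instruction in 5.2, "hold dose until toxicity resolves to ≤ grade 1, then resume at dose given in prior cycle", is compatible with a reduced dose if the prior cycle was already at 150 mg. Footnote d to Table 5.4, "The decision to withhold or permanently discontinue pembrolizumab is at the discretion of the investigator or treating physician", attaches only to type 1 diabetes or hyperglycemia and to grade 3-4 hypophysitis and hyperthyroidism.

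On grade, a reader might infer that grade 4 and 5 events would go unhandled. They would not. Most Table 5.4 rows stop pembrolizumab at grade 4, serious suspected reactions go to the DSMC, and related deaths must reach its chair within one business day. These safeguards protect patients but do not say how to count for 8.2 or which instruction to follow.

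A reader might also infer from 5.1 that a 25% cut could not reduce toxicity, because it describes exposures "within the range of exposures shown in the melanoma studies of 2 and 10 mg/kg to provide similar efficacy and safety". That statement concerns melanoma studies, not this combination. Also, 150 mg is below 2 mg/kg for anyone over 75 kg (150 / 2 = 75), outside the doses compared. The documents do not settle whether the cut would help.

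**Conclusion.** The inconsistency is real and should be fixed. For immune-related events, 8.2 and 5.2.2 give incompatible instructions. For non-immune events the tension is narrower and rests on three words. Section 5.2 adds to the inconsistency by telling the team to reduce the responsible agent. The missing *or higher* is a secondary wording fault whose intended meaning is fairly clear.

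The size is qualitative. The documents give no pembrolizumab-related toxicity rates by grade, so neither the frequency of a trigger nor the effect of the grade wording can be computed. Sample size and stated error rates are unaffected.

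A reader might infer that the between-arm comparison is already compromised. It is not: a dose difference between arms would arise only if one arm met the trigger, the cut was confined to that arm, and the team followed 8.2 over 5.2.2.

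The conclusion assumes that the words *clearly related to pembrolizumab* include immune-related toxicity, as their plain meaning suggests, and that no unreproduced guidance sets precedence.

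**What to change.** 1. In 8.2, write *grade 3 or higher*.
2. In 8.2, replace the 75% reduction with an action consistent with 5.2.2. For example: hold enrolment in that arm pending DSMC review, and manage individual patients under Table 5.4. Appendix 2 already provides for notifying the DSMC when enrolment is held for safety.
3. In 5.2, limit the dose-reduction wording, including the statement that both drugs may be reduced, to vorinostat.
4. Reconcile the longer intervals in 5.1 and Table 5.6 with the no-change-of-schedule sentence, by naming them as exceptions or removing them.

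The cost is a few lines of amendment. The trigger may fire slightly more often, and a hold would slow a trial expecting ten eligible patients a year (8.1.4). If a hold lasted six weeks, the DSMC meeting interval in 7.3.6, about 10 × 6/52 ≈ 1.2 eligible patients would present across both arms meanwhile. The amendment should also say whether randomization to the other arm continues during a hold.
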